STUDY TITLE: Oral Penicillin Challenge in the Pediatric Emergency Department

NCT number: NCT03404804

Document date: 1aug22 last continuing review approval

PRINCIPAL INVESTIGATOR: [name], DO, MS

STUDY TITLE: Oral Penicillin Challenge in the Pediatric Emergency Department

A. PURPOSE OF THE STUDY

The purpose of this study is to utilize a parent-reported penicillin allergy questionnaire in a pediatric emergency department (PED) and demonstrate that providers will administer, and families will be willing to receive an oral penicillin challenge in those children deemed to have non-allergic and low-risk symptoms of true penicillin allergy.

B. HYPOTHESES / SPECIFIC AIMS

Aim 1: Demonstrate that a low-risk group of children with reported penicillin allergy will complete an oral penicillin challenge during a pediatric emergency department visit.

Hypothesis 1a: Providers will administer an oral penicillin challenge in the PED to children identified as having non-allergic and low-risk allergy symptoms.

Hypothesis 1b: Children with non-allergic and low-risk allergy symptoms will complete an oral penicillin challenge in the PED.

Aim 2: Conduct follow-up one day after oral challenge for all children and seven days after oral challenge for patients discharged with a prescription antibiotic to determine if a delayed or T-Cell mediated reaction occurs after exposure to multiple doses of penicillin or any other antibiotic prescribed at discharge.

Hypothesis 2a: Next day contact will be possible for over 95% of children who complete an oral challenge to demonstrate the ability to evaluate symptoms after PED discharge.

Hypothesis 2b: Seven-day follow-up will be completed in at least 90% of children who are discharged on a penicillin or other antibiotic to demonstrate the ability to monitor for delayed or T-Cell mediated reaction following the administration of multiple doses of penicillin.

Aim 3: Examine health care outcomes and prescription-related costs associated with illness treatment plans in children who are de-labeled as penicillin allergic after an oral challenge.

Hypothesis 3a: Health care outcomes (allergic reactions, number of illnesses, antibiotics prescribed, and ER/Urgent Care/Primary care visits) will be similar between children de-labeled as penicillin allergic compared to the general population.

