- 9) If there is a serious or anaphylactic reaction, emergency medicine will be given right away. The medicine is called epinephrine and comes in an Epi-Pen. Additional medications that could also be given include steroids, Benadryl, Zantac, and IV fluids. If a reaction occurs that requires emergency medicine the patient or the patient’s insurance are liable for the cost of this continued treatment. Their liability also includes any copay that may associated with the use of their insurance or if insurance does not cover the inpatient hospitalization. The potential costs for treating a reaction in which a patient is hospitalized may be thousands of dollars. However, we believe the risk of this occurrence to be very low as the incidence of true IgE mediated penicillin allergy is estimated to be in the range of 0.004% to 0.015%.^{21,22} Additionally, those children deemed low-risk on our questionnaire, likely never had an IgE mediated allergic reaction to begin with and are most likely falsely labeled as penicillin allergic. Families are also notified in the Oral Challenge consent and assent to call 9-1-1 and seek immediate medical attention if any serious reaction occurs after their child leaves the ED.
- 10) At the end of the visit the diagnosis will be recorded, and treatment/discharge will continue at the discretion of the PED physician/nurse practitioner/physician assistant . All patients who receive an oral challenge will be given an Allergy Oral Challenge Information sheet.
- 11) If a child is negative after oral challenge and has no need for an antibiotic at the time of discharge, the child will be discharged home.
- 12) If a child is negative after oral challenge and treatment would indicate a penicillin antibiotic, the child will be discharged home with a penicillin antibiotic.
- 13) Family contact information will be obtained in the questionnaire and utilized to complete follow-up phone calls after PED oral challenge.
- 14) The patient’s PMD (primary medical doctor) and pharmacy of record will be notified of the testing and results via fax within 7 days. Fax confirmations will be kept by the study team in the patient’s research file.

Aim 2: Conduct follow-up one day after oral challenge for all children and seven days after oral challenge for patients discharged with a prescription antibiotic to determine if a delayed or T-Cell mediated reaction occurs after exposure to multiple doses of penicillin or any other antibiotic prescribed at discharge.

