
Design/setting and study population:

This study will include all children from Aim 1 who underwent an oral challenge in the PED after being determined to have low-risk symptoms on the allergy questionnaire.

Study Procedure (Figure 1, Aim 2)

- 1) A follow-up phone call will be made to all families whose child received an oral challenge.
- 2) If a family receives a one-time dose of antibiotic but does not receive a prescription for a penicillin antibiotic then they will be called on day 1 by a research team member who will administer a 5-minute allergy questionnaire that will review any possible symptoms of allergic reaction following the ED visit.
- 3) If a family receives a penicillin antibiotic prescription following the oral challenge, then they will be called on days 1 and 7 by a research team member for a 5-minute allergy questionnaire that will review any possible symptoms of allergic reaction following the ED visit.
- 4) The patient's primary medical provider will also be notified of the oral challenge results for both groups of patients via fax within 7 days of the oral challenge date.

Aim 3: Examine health care outcomes and prescription-related costs associated with illness treatment plans in children who are de-labeled as penicillin allergic after an oral challenge.**Design/setting and study population:**

This study will include children identified as having low-risk symptoms of allergy from Aim 1 who underwent an oral challenge (Group 1), and those who did not undergo an oral challenge in the PED (Group 2).

Study Procedure (Figure 1, Aim 3)

- 1) A follow-up 5-minute phone survey will be completed by research staff to the family. This follow-up will occur after their initial PED visit at 6 and 12 months.
- 2) The follow-up survey will include questions on health care outcomes since the PED visit that include but are not limited to: the number and type of diagnosed infections, number and type of antibiotics given, and allergic reaction history.

E. TOTAL NUMBER OF HUMAN RESEARCH PARTICIPANTS PROPOSED FOR THIS STUDY AT THIS SITE AND GLOBALLY. WHAT ARE THESE NUMBERS BASED ON?

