We have determined that we need 100 low-risk patients to complete the oral challenge at each of the three sites participating including here at Children's Hospital of Wisconsin. We will consent for questionnaire-screening approximately 500 children to achieve that number. This number is based off of our previous study; during that study 50 patients were approached per month for survey participation, 80% (40) agreed to participation, and 25% (10) of patients were found to have high-risk symptoms of allergy and thus were found to be ineligible. If 50% of patients with low-risk symptoms will have either provider/family refusal to oral challenge this will leave approximately 15 patients per month to complete an oral challenge and complete this portion of the study in approximately 7 months.

F. DRUGS OR PROCEDURES

Patient's family or guardian will be asked to answer an allergy symptom questionnaire that will be administered via an iPad. Patient's charts who are between the ages of 2-16 whose family has indicated an interest in allergy oral challenge will be reviewed.

If a child is eligible as defined in the questionnaire for allergy oral challenge and the family completes the challenge, then a gift card in the amount of \$50 will be provided for their time.

If a family completes all the telephone follow-up questionnaires at 6 and 12 months they will be mailed a \$25 gift card at the conclusion of each of the follow-up calls. (total of \$50 in follow-up stipends for full participation over one year.)

The allergy challenge consists of an oral amoxicillin challenge in the PED. A nurse will administer the oral challenge and will also be present during the process all of which will occur in the PED.

A follow up telephone survey monitoring for any adverse side effects/allergic reactions will be completed within 24 hours of the allergy oral challenge. If a patient receives a prescription for a penicillin or any other antibiotic then a follow up call will be made to monitor for any adverse side effects/allergic reactions at 7 days as well. Patients will also receive discharge instructions relevant to the study with phone numbers to call with questions.

A follow-up 5-minute phone survey will be completed by research staff to families of groups after their initial PED visit at 6 and 12 months. PI will review these results monthly or as relevant (notified by the study team) to monitor the long-term outcomes and safety of the protocol.

G. RISK CATEGORY:

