3) Research staff is present in the PED 16 hours per day on weekdays and 10 hours per day on weekends allowing for more than sufficient coverage to meet enrollment goals. We will limit administration of the oral challenge to 3 patients per day in an attempt to limit PED flow disruption. Administration of the questionnaire alone should not be disruptive to flow.

The appropriately trained research personnel will be identified in the registration page of this submission.

O. Statistical Analysis plan

Data collection and Management:

All children will be assigned a unique study ID number. Responses to the allergy questionnaire and oral challenge will be captured on a tablet computer. Data will be entered into RedCap (<http://www.project-redcap.org/>). Additional data points include child’s age in years, child’s sex, race/ethnicity (determined by parent and consistent with NIH guidelines) and visit number.

For children who receive an oral challenge, additional data will include the time of medication administration and time of discharge from the PED. The details of any reaction that occurred and corresponding treatment will also be captured. Final ED disposition will be recorded, and home contact information confirmed for follow-up.

Data Analysis:

Descriptive statistics will be used to summarize baseline patient characteristics, allergy questionnaire, and oral challenge data. The percentage of patients who are eligible for oral challenge will be determined. The percent

of patients/families that refuse an oral challenge or that have providers who are unwilling to conduct an oral challenge in the PED will be documented. The frequency of positive oral challenges will be analyzed and reported using a 95% confidence interval. Descriptive statistics will be used to summarize day 1 and 7 patient characteristics and follow-up questionnaire data. The percentage of patients that are lost to follow-up after an oral challenge will be determined. The frequency of delayed allergic reactions after oral challenge will be analyzed and reported using a 95% confidence interval. SPSS version 22 will be used to perform all analyses. SPSS version 22 will be used to perform all analyses.

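### Hypothesis 2b and the delayed-reaction frequency pool penicillin courses with other discharge antibiotics, and the sections disagree on who receives the day-7 call

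*Combined protocol and SAP*

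**What the plan says.** Aim 2 (Section B, repeated in Section D) looks for delayed or T-cell mediated reactions "after exposure to multiple doses of penicillin or any other antibiotic prescribed at discharge". Its scope is therefore wider than penicillin by design.

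Hypothesis 2b (Section B) sets its target as: "Seven-day follow-up will be completed in at least 90% of children who are discharged on a penicillin or other antibiotic". The same sentence gives the purpose as being able to "monitor for delayed or T-Cell mediated reaction following the administration of multiple doses of penicillin".

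Section O, Data Analysis, has one line on the outcome: "The frequency of delayed allergic reactions after oral challenge will be analyzed and reported using a 95% confidence interval". It gives no definition of a delayed reaction, no time window, no denominator, no split by discharge drug and no rule for attributing a reaction to a drug. The data items listed in Section O for challenged children include administration and discharge times, reaction details and treatment, and final disposition. The antibiotic prescribed at discharge is not listed. Antibiotic type is named only in the Aim 3 survey at 6 and 12 months.

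On the day-7 call, the Aim 2 Study Procedure (Section D, step 3) says: "If a family receives a penicillin antibiotic prescription following the oral challenge, then they will be called on days 1 and 7". Step 2 says that a family that "does not receive a prescription for a penicillin antibiotic then they will be called on day 1". Section F says otherwise: "If a patient receives a prescription for a penicillin or any other antibiotic then a follow up call will be made", with that call placed at 7 days. The Aim 2 statement and Hypothesis 2b agree with Section F.

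**The concern.** Three exposures sit under one reported frequency: a single amoxicillin dose; that dose plus a penicillin course; and that dose plus a course of something else. Only the second says anything about repeated penicillin dosing. A reaction in the third group could be due to either drug, and the planned report would not show that it arose there.

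Pooling can mislead in two ways. A reaction during another antibiotic enters the figure reported for the penicillin challenge. Conversely, reaction-free children on another antibiotic enlarge the group that appears to support the safety of repeated penicillin doses.

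Hypothesis 2b has the same mismatch within one sentence. The target can be met while follow-up among penicillin-course children, the group its purpose concerns, is below 90%.

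The conflict over day-7 calls adds to this. If the Aim 2 procedure is followed, children on another antibiotic are in the Hypothesis 2b denominator with no scheduled day-7 call.

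**Working it through.** **Inputs.** Section O, Sample Size Justification: 50 challenged children, about 20% discharged with a prescription antibiotic, class not stated. Hypothesis 2b: target of at least 90%. Section E gives a different number of challenges, 100 per site. The number k of prescription children on a non-penicillin drug is not in the documents. It is an assumption here and is shown over a range.

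**Plan's own figures.** 50 × 0.20 = 10 children with a prescription, as stated. The interval quoted in Section C for 100 of 100 negative challenges (96.4% to 100%) reproduces as an exact Clopper-Pearson interval: lower limit 0.025^(1/100) = 0.9638. The same method is used below.

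**Formulas for 10 prescription children, k of them on another drug.**
- Penicillin courses: 10 − k.
- Highest pooled day-7 rate from scheduled calls if the Aim 2 procedure is followed: (10 − k)/10.
- If all prescription children are called, the pooled target needs 9 of 10. If the one child missed was on penicillin, penicillin-course follow-up is (9 − k)/(10 − k).
- Upper exact 95% limit with zero reactions among n children: 1 − 0.025^(1/n).

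| k (assumed) | Penicillin courses | Highest pooled rate, penicillin-only calls | Penicillin-course follow-up when pooled is 9/10 | Upper limit, 0 reactions, penicillin courses |
|---|---|---|---|---|
| 0 | 10 | 10/10 | 9/10 (90%) | 30.8% |
| 1 | 9 | 9/10 | 8/9 (88.9%) | 33.6% |
| 2 | 8 | 8/10 | 7/8 (87.5%) | 36.9% |
| 3 | 7 | 7/10 | 6/7 (85.7%) | 41.0% |
| 5 | 5 | 5/10 | 4/5 (80%) | 52.2% |

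The pooled group of 10 with zero reactions has an upper limit of 30.8% whatever k is. The third and fourth columns are alternatives: they describe the two conflicting call schedules.

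**Effect on the overall frequency.** One reaction during another antibiotic, taking all challenged children as the denominator (Section O does not name one), moves the result from 0/50 (0% to 7.11%) to 1/50 = 2% (0.05% to 10.65%). With 100 children it moves from 0/100 (0% to 3.62%) to 1/100 = 1% (0.03% to 5.45%).

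**With 100 challenged children.** 100 × 0.20 = 20 prescriptions, and the target needs 18. If 6 are on another drug, 18/20 pooled can accompany 12/14 (85.7%) on penicillin courses, and the zero-reaction upper limit is 23.2% on 14 courses against 16.8% on 20. Under penicillin-only calls, 3 or more on another drug cap the pooled rate at 17/20 (85%).

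**The case against.** Covering other antibiotics is a deliberate choice in Aim 2, and counting every reaction after the challenge is a defensible, conservative safety summary. Every child in the analysis took amoxicillin, so a later reaction cannot be assigned to the other drug with certainty. This stands, and it is why the overall frequency should be kept. It does not remove the need to show which exposure each reaction followed.

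The numbers are small, the endpoint is descriptive with no test or decision threshold, and k may be zero: Section D (Aim 1, steps 11 and 12) describes only no antibiotic or a penicillin after a negative challenge. Other drugs enter through provider discretion in step 10, although Aim 2, Hypothesis 2b and Section F all name them. Investigators review data after every reaction, so case-level description is feasible. All of this limits the size of the problem. The mismatch in Hypothesis 2b and the conflict over calls are in the text regardless of k.

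A reader might infer that the plan blames penicillin for reactions to another drug. Section O does not say so: it leaves the endpoint undefined, and Hypothesis 2b is a contact-completion target that attributes nothing. A reader might also infer that such a reaction would give a child back a penicillin label. The documents set no such rule; they provide for faxing the test results to the primary doctor and pharmacy, and a group percentage does not label an individual. Lastly, a day-5 rash on another drug might be assumed to reach the analysis; under steps 2 and 3 of the Aim 2 procedure no scheduled Aim 2 call would collect it.

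**Conclusion.** The point holds as a matter of reporting and consistency. The Hypothesis 2b denominator is wider than its stated purpose, the single delayed-reaction frequency pools three exposures without a way to separate them, and the sections contradict each other on who is called on day 7.

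The size depends on k, which the documents do not give. For any k from 1 to 9, the pooled target can be met at 9/10 while penicillin-course follow-up is below 90%. At an assumed k of 3, the evidence on repeated penicillin dosing rests on 7 children rather than 10. Under penicillin-only calls, scheduled contact cannot meet the pooled target once k is 2 or more.

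This affects the interpretation of a small descriptive endpoint. It does not affect power, and it does not show that any reaction would be wrongly attributed. The change should be made because it costs little and the missing field would otherwise have to be recovered from charts.

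**What to change.** 1. Reconcile the day-7 call population across Section B (Aim 2 and Hypothesis 2b), Section D (the Aim 2 statement and procedure steps 2 and 3) and Section F, so that one population applies throughout.
2. Define delayed reaction, its time window and its denominator in Section O.
3. Record the discharge antibiotic for every challenged child as penicillin, other or none.
4. Keep the overall delayed-reaction frequency, and also report it by this code with exact 95% intervals. Base any statement about multiple penicillin doses on penicillin-course children only.
5. Report the Hypothesis 2b completion rate for penicillin courses, with the any-antibiotic rate as a second figure if those calls are made.

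The cost is one coded field, one table split and a few lines of text. The Hypothesis 2b denominator becomes smaller and the intervals on penicillin courses wider. No change in sample size is needed.

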Hypothesis 3b: Prescription-related costs associated with illness treatment plans will be significantly less in children de-labeled as penicillin allergic.

C. BACKGROUND, SIGNIFICANCE, AND RATIONALE

Children often present to the pediatric emergency department with a parent reported allergy to medications. Allergy to an antibiotic in the penicillin family (hereafter termed penicillin) is the most commonly reported medication allergy, reported in 5-20% of patients.¹⁻⁶ Since physicians and advanced practice providers (hereafter termed providers) rely on these patient/parent reported allergies when making treatment decisions, a large group of patients are denied first-line antibiotic therapy due to misunderstood or misdiagnosed penicillin allergy.⁷ As a consequence, patients are prescribed second or third line medications that are more expensive and not the antibiotic of choice for their bacterial infection.^{8,9} An example of the health risks associated with

reported penicillin allergy was highlighted by Macy et al who found that, “A penicillin “allergy” history, although often inaccurate, is not a benign finding at hospital admission. Subjects with a penicillin “allergy” history spend significantly more time in the hospital, are exposed to significantly more antibiotics associated with Clostridium difficile (C. diff) and Vancomycin-Resistant Enterococci (VRE) and are associated with increased hospital use.”⁹ Additionally it has been shown that de-labelling patients reported to have penicillin allergy can lead to decreased prescription costs with very low rates of subsequent adverse reactions.¹⁰ Specific to penicillin allergy, greater than 95% of patients may actually tolerate a penicillin, either because they were never allergic or because they had an earlier allergy that subsequently resolved.¹¹

Our prior work utilized a novel structured penicillin allergy questionnaire in the PED and found that 76% of the children with penicillin allergy reported by families had exclusively low-risk allergy symptoms for true allergy (Table 1).¹² These symptoms were often adverse reactions, inconsistent with true allergy.¹³⁻¹⁵

Table 1: Categorization of Allergy Symptoms

Low Risk Group		High Risk Group	
Non-Allergic Symptoms	Low-Risk Symptoms	High-Risk Symptoms	
Runny nose	Rash	Facial swelling	Seizures
Diarrhea	Itching	Difficulty breathing	Rash*
Headache	Dizziness	Lip swelling	Itching*
Vomiting with med administration	Vomiting	Wheezing	Vomiting**

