Objective

Our primary objective is to demonstrate the feasibility of utilizing a novel penicillin allergy questionnaire in the PED to identify a low-risk group of patients who will complete an oral challenge in the PED to test for an IgE-mediated allergic reaction. This project will begin as a single site feasibility study, however including up to 2 other collaborative sites for enrollment has been favorably discussed. We do not anticipate this to be a single IRB scenario and will submit a timely comprehensive amendment if plans become concrete and the initial data here proves reliable.

Our secondary objective is to examine whether health care outcomes and prescription-related costs are comparable between children who are de-labeled as penicillin allergic after an oral challenge compared to a standard of care group who are not challenged in the PED.

Aim 1: Demonstrate that a low-risk group of children with reported penicillin allergy will complete an oral penicillin challenge during a pediatric emergency department visit.

Design/setting:

This will be a prospective study of children (2-16) presenting to the PED at the Children's Hospital of Wisconsin with a child or parent reported allergy to penicillin.

Population:

[figure not shown]
Inclusion Criteria: Children aged 2-16 with a parent/guardian (hereafter termed parent) reported history of allergy to a penicillin antibiotic in which the reported allergic reaction occurred at least twelve months prior to the current PED visit.

Exclusion Criteria: Children will be excluded:

- If they have a history of severe developmental delay or inability to communicate the effects of an allergic reaction (non-verbal). ED care team discretion can be utilized to determine ability to proceed with study with regards to developmental delay.
- History of a severe allergic reaction to skin tests
- Anaphylaxis in the past six weeks
- Current pregnancy
- Child is currently on a beta blocker medication
- Children who present to the PED with a rash
- Children who present with multiple episodes of vomiting on day of presentation
- Children presenting to the ED for asthma exacerbation
- Patients deemed too acutely ill for participation as deemed by the ED patient care team
- Non-English speaking families
- Wards of the state, in foster care or police custody or detention will be excluded.

Study Procedure (Figure 1):

Figure 1: Study Procedures for Full Protocol

¹Red boxes indicate oral-challenge-only study procedures

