Descriptive characteristics will also be used to summarize the baseline patient characteristics and follow-up questionnaire responses for months 6 and 12 of the children who underwent the oral challenge in Aim 1. We will then conduct a three-level economic cost savings analysis. First, in order to calculate the potential cost savings if amoxicillin is filled for all penicillin allergic de-labelled patients, the median retail price of each non-penicillin antibiotic filled will be compared to the median retail price of amoxicillin. Second, we will calculate the cost avoidance savings assuming that patients who fill any amoxicillin/penicillin prescriptions would have filled cefdinir in its place. Lastly, we will extrapolate the total cost savings potentially generated by the approximately 6,700 patients per year treated in our PED who report penicillin allergy.

Sample Size Justification/Power Analysis:

We have determined that we need 50 patients to complete the oral challenge for the feasibility study to be complete. We will consent for questionnaire-screening approximately 250 children to achieve that number. This number is based off of our previous study; during that study 50 patients were approached per month for survey participation, 80% (40) agreed to participation, and 25% (10) of patients were found have high-risk symptoms of allergy and thus were found to be ineligible. Assuming that 50% of patients with low-risk symptoms will have either provider/family refusal to oral challenge this will leave approximately 15 patients per month to complete an oral challenge. Of the 50 children who complete the oral challenge, we estimate that 40 patients will receive a one-time oral challenge and 10 patients will receive an oral challenge and be sent home with a prescription. This estimation is based off of our previous study where approximately 20% of children who were eligible and willing to be tested were discharged home with a prescription antibiotic. If we are able to reach our enrollment goal prior to approaching 500 patients, we will end the feasibility study.

P. FINANCIAL RELATIONSHIPS

The study is funded with internal funds from the section of Pediatric Emergency Medicine and a grant from the Children's Research Institute which support the costs of accomplishing the oral challenges and other associated project costs.

Q. ADVERTISEMENTS / FLIERS

N/A

R. BIBLIOGRAPHY (*list pertinent literature references*)

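### Hypothesis 3a and the secondary objective name different comparators, and Section O uses neither, so the secondary objective has no between-group estimate

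*Combined protocol and SAP*

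**What the plan says.** **Hypotheses (Section B).** Hypothesis 3a lists its outcomes as "Health care outcomes (allergic reactions, number of illnesses, antibiotics prescribed, and ER/Urgent Care/Primary care visits"), and says that they "will be similar between children de-labeled as penicillin allergic compared to the general population". Hypothesis 3b reads "Prescription-related costs associated with illness treatment plans will be significantly less in children de-labeled as penicillin allergic"; it names no comparator.

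**Secondary objective (Section D, Objective).** Health care outcomes and prescription costs in children de-labeled after a challenge are to be "compared to a standard of care group who are not challenged in the PED".

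**Aim 3 design (Section D).** Group 1 is the low-risk children who were challenged. The other group is "those who did not undergo an oral challenge in the PED (Group 2"). The survey items "include but are not limited to: the number and type of diagnosed infections, number and type of antibiotics given, and allergic reaction history".

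**Follow-up (Section F).** The phone survey goes to "families of groups after their initial PED visit at 6 and 12 months".

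**Analysis (Section O, Data Analysis).** For this period the plan gives descriptive summaries of "follow-up questionnaire responses for months 6 and 12 of the children who underwent the oral challenge in Aim 1". A three-level cost analysis follows. Level 1 sets the median retail price of each non-penicillin antibiotic filled against that of amoxicillin. Level 2 supposes that every amoxicillin or penicillin fill would otherwise have been cefdinir. Level 3 scales the saving up to about 6,700 patients a year.

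**The concern.** Three parts of one document describe three different things: a comparison with the general population, a comparison with an unchallenged group, and a one-group description. Only the last has an analysis. An analyst who follows Section O exactly will report Group 1 at months 6 and 12 and then a modelled saving.

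That output cannot answer the secondary objective. *Similar* (3a) has no comparator data and no criterion. *Significantly less* (3b) would rest on a substitution that the plan assumes rather than on costs observed in another group. In level 2 the saving follows largely from the assumed price gap. Any data gathered from Group 2 families would have no planned use, and a comparison added later would be chosen after the data were seen.

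**Working it through.** **1. The passages side by side**

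| Place | Comparator | Analysis given |
|---|---|---|
| Section B, Hypothesis 3a | General population; no data source | None |
| Section B, Hypothesis 3b | Not named | None |
| Section D, secondary objective | Standard-of-care children not challenged | None |
| Section D, Aim 3 design | Group 2, low-risk and not challenged | None |
| Section F | Calls to the groups at 6 and 12 months | None |
| Section O | None; challenged children only | Descriptive summary; modelled costs |

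Section O does promise 95% confidence intervals for positive challenges and for delayed reactions. It promises none for Aim 3. It also documents refusals, which describes unchallenged children at the index visit but not at 6 or 12 months.

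**2. The cost levels.** Level 1 uses observed fills of non-penicillin antibiotics; only its alternative (amoxicillin for all) is assumed. Level 2 uses observed penicillin fills and an assumed alternative (cefdinir). Level 3 is an extrapolation. None compares observed costs between two groups, and none has an interval.

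**3. The plan's own figure.** Section O's enrolment rates reproduce: 50 approached × 0.80 = 40 agreeing; 40 × 0.75 = 30 low-risk; 30 × 0.50 = 15 challenged per month, as stated.

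**4. How large Group 2 could be.** No size is stated, and the documents imply two.
- From the 50% refusal assumption: 30 − 15 = 15 unchallenged per month, so Group 2 is about as large as Group 1.
- From the questionnaire-consent totals (about 250 for 50 completers in Section O; about 500 in Section E, read here as per site, for 100 completers): 250 × 0.75 − 50 = 137.5, about 138; 500 × 0.75 − 100 = 275; for three sites, 3 × 275 = 825.

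**5. Illustrative precision.** The 95% half-width for a mean difference, in SD units, is t(0.975, n1 + n2 − 2) × √(1/n1 + 1/n2), with full retention and a common SD.

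| Challenged | Unchallenged | t × root | Half-width (SD) |
|---|---|---|---|
| 50 (Section O) | 50 | 1.985 × 0.2000 | 0.40 |
| 50 | 138 | 1.973 × 0.1651 | 0.33 |
| 100 (one site, Section E) | 100 | 1.972 × 0.1414 | 0.28 |
| 100 | 275 | 1.966 × 0.1168 | 0.23 |
| 300 (three sites, Section E) | 300 | 1.964 × 0.0816 | 0.16 |
| 300 | 825 | 1.962 × 0.0674 | 0.13 |

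The gap in the plan does not depend on these figures. They show only what a comparison could deliver.

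**The case against.** The strongest reply is that this is a feasibility study. Its primary objective is untouched, Aim 3 is secondary, and a descriptive summary is a reasonable ambition for it. Section O also words the cost levels conditionally, so it does not present them as observed savings. And because Hypothesis 3b names no comparator, a modelled counterfactual does not contradict 3b itself; the conflict is with the secondary objective. All of this stands, and it limits the weight of the point. It does not remove it: the sponsor wrote a comparative objective and comparative hypotheses, and if description is enough the text should say so.

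A reader might infer more than the documents support:

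- **That Group 2 will not be followed, or lacks consent.** Section F plans the calls. The visible text puts permission for Aim 3 contact in the oral-challenge consent (Section D, Aim 1 steps 2 and 5; Section N), but the consent forms are not available here. It is a question to settle, not a finding.
- **That adding the comparison needs only new text in Section O.** For the same reason this cannot be assumed.
- **That the study is too small to show similarity.** The documents give no margin, event rate or Group 2 size, and the answer changes with the size assumed.
- **That the cost analysis is wholly hypothetical.** Levels 1 and 2 start from antibiotics actually filled.

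**Conclusion.** The point holds on the text and should be fixed. The two named comparators conflict, Section O uses neither, and the between-group estimate required by the secondary objective is wholly absent. The cost levels cannot show that costs are significantly less than in an observed group.

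If the comparison were made, its precision would be modest with 50 or 100 challenged children (half-widths from 0.23 to 0.40 SD) and better with 300 (0.13 to 0.16 SD). This rests on inferred Group 2 sizes, full retention, a common SD and reading the 500 in Section E as per site. It takes no account of confounding: Group 2 arises largely from provider or family refusal, so the groups may differ in ways that the survey does not capture. Aims 1 and 2 are unaffected.

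**What to change.** Choose one of two repairs.

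**Repair 1: Group 2 can be followed.**
- *Confirm first* that consent and contact details cover Group 2. Contact details are collected in the questionnaire, but their stated use is calls after a challenge (Section D, Aim 1 step 13), and Section O confirms home contact under challenged children. Where nursing gave the questionnaire, research consent is sought for the challenge alone, so a refusing family has no research consent described.
- *Confirm* that the survey asks about emergency, urgent care and primary care visits. They are a 3a outcome but are not among the listed items, although that list is open-ended.
- *Name Group 2* as the comparator in Section O and in Hypotheses 3a and 3b.
- *State whether Group 1* means all challenged children, as in the Aim 3 design, or only de-labeled (challenge-negative) children, as in the hypotheses.
- *Report differences with 95% confidence intervals* for each 3a outcome and for prescription cost, priced the same way in both groups. A Newcombe interval suits allergic reactions; bootstrap intervals suit mean counts and cost.
- *Show* baseline characteristics side by side and the reasons for no challenge. State that the comparison is non-randomised and confounded by refusal.
- *Replace* the *similar* and *significantly less* wording with estimation.

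Cost: edits to Section O and the hypotheses, a two-group summary, and possibly a change to consent and to the survey. Residual confounding remains.

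**Repair 2: Group 2 will not be followed.** Reword the secondary objective and Hypotheses 3a and 3b as descriptive of challenged children, and present costs as modelled scenarios. Cost: text only, but the comparison is given up.
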